13.1.3 PK Analyses

By-subject listing of pharmacokinetic parameters will be provided. The values of the pharmacokinetic parameters will also be summarized using descriptive statistics (N, arithmetic mean, standard deviation, standard error, minimum, median, maximum, percent coefficient of variation, geometric mean, and geometric percent coefficient of variation) for each cycle. Also, when appropriate, graphical representations (i.e., scatter plots, box plots, etc.) may be used to visualize the results.

The effect of durvalumab on the PK of CC-486 will be assessed using graphic comparison and descriptive stats.

cc

13.2 Durvalumab

13.2.1 Plasma concentrations

By-subject listing of pharmacokinetic blood sample collection times as well as derived sampling time deviations will be provided. Durvalumab serum concentrations will be summarized using descriptive statistics (N, arithmetic mean, standard deviation, standard error, minimum, median, maximum, percent coefficient of variation, geometric mean, and geometric percent coefficient of variation).

Concentrations that are below the limit of quantitation (BLQ) will be treated as zero for the computation of descriptive statistics. Missing concentrations and concentrations from blood

samples collected more than $\pm 10\%$ of nominal time will be omitted from the calculation of descriptive statistics.

Individual subject concentration-time data and mean concentration-time data for each cycle will be graphically presented on linear and semi-logarithmic scales.

Following dose administration, pre-dose samples that are BLQ or missing will be assigned a numerical value of zero for the calculation of AUC. Following the first administration, any anomalous concentration values observed at pre-dose will be identified in the study report and used for the computation of AUC. Pharmacokinetic parameters will be computed if the anomalous value is not greater than 5% of the C_{max} . If the anomalous value is greater than 5% of C_{max} , the computed PK parameters for the given subject will be dropped from the PK analysis.

Any other BLQ concentrations will be assigned a value of zero if they precede quantifiable samples in the initial portion of the profile. A BLQ value that occurs between quantifiable data points, especially prior to C_{max} , will be evaluated to determine if an assigned concentration of zero makes sense, or if reanalysis or exclusion of the data is warranted. Following C_{max} , BLQ values embedded between two quantifiable data points will be treated as missing when calculating AUC. Values below the quantifiable limit, occurring at the end of the collection interval (after the last quantifiable concentration), will be treated as missing data. If consecutive BLQ concentrations are followed by quantifiable concentrations in the terminal portion of the concentration curve, these quantified values will be excluded from the PK analysis by assigning them a value of missing, unless otherwise warranted by the concentration-time profile. For the purpose of analysis, these trailing BLQ values may be designated as zero in the dataset if the PK program used to do the analysis (such as WinNonlin[®]) will treat trailing zero values as missing when calculating AUC.

Actual sampling times will be used in the calculations of pharmacokinetic parameters that will be derived using non-compartmental (NCA) methods with Phoenix[™] WinNonlin[®] Professional Version 6.4, or higher, (Pharsight[®], a Certara[™] company, St. Louis, Missouri). Graphics may be prepared with SAS Version 9.3, or higher; or Excel 2007, or higher; Phoenix[™] WinNonlin[®] Professional 6.4, or higher.

13.2.2 PK Parameter

The following PK parameters will be calculated for durvalumab on Cycle 1:

$AUC_{0-\infty}$ Area under the serum concentration-time curve from Time 0 extrapolated to infinity, calculated as $[AUC_{0-t} + C_t/\lambda_z]$. C_t is the last quantifiable concentration. No AUC extrapolation will be performed with unreliable λ_z . If %AUC_{extrap} is $\geq 25\%$, $AUC_{0-\infty}$ will not be reported.

AUC_{0-t} Area under the serum concentration-time curve from Time 0 to the time of the last quantifiable concentration, calculated by linear trapezoidal method when concentrations are increasing and the logarithmic trapezoidal method when concentrations are decreasing.

C_{max} Maximum observed serum concentration, obtained directly from the observed concentration versus time data.

| | |
|-----------|--|
| T_{max} | Time to C_{max} , obtained directly from the observed concentration versus time data. |
| $t_{1/2}$ | Terminal phase half-life in serum, calculated as $[(\ln 2)/\lambda_z]$. $t_{1/2}$ will only be calculated when a reliable estimate for λ_z can be obtained. |
| CL | Total clearance, calculated as $[Dose/AUC_{0-\infty}]$. |
| V_z | Volume of distribution, calculated as $[(CL)/\lambda_z]$. |

The following PK parameters will be calculated for diagnostic purposes and listed, but they will not be summarized:

| | |
|------------------------|--|
| λ_z | Apparent terminal rate constant, calculated by linear regression of the terminal portion of the log-concentration versus time curve in serum. Visual assessment will be used to identify the terminal linear phase of the concentration versus time profile. A minimum of three data points will be used for calculation. λ_z will not be estimated if the terminal phase of the log-concentration versus time profile does not exhibit a linear decline phase, or if the regression coefficient < 0.8 . |
| λ_z lower | Lower limit of time (h) included in the calculation of λ_z . |
| λ_z N | Number of data points used in the calculation of λ_z . |
| λ_z upper | Upper limit of time (h) included in the calculation of λ_z . |
| Rsq | Regression coefficient for calculation of λ_z . |
| %AUC _{extrap} | Percentage of AUC _{0-∞} due to extrapolation from the last quantifiable time point to infinity. |

The following PK parameters will be calculated for durvalumab on Cycle 2:

| | |
|--------------------|---|
| AUC _{0-t} | Area under the serum concentration-time curve from Time 0 to the time of the last quantifiable concentration, calculated by linear trapezoidal method when concentrations are increasing and the logarithmic trapezoidal method when concentrations are decreasing. |
| C_{max} | Maximum observed serum concentration obtained directly from the observed concentration versus time data. |
| T_{max} | Time to C_{max} , obtained directly from the observed concentration versus time data. |

Note: only the 3 PK parameters listed above will be calculated as durvalumab is expected to not be at BLQ level at the start of Cycle 2.

13.2.3 PK Analyses

By-subject listing of pharmacokinetic parameters will be provided. The values of the pharmacokinetic parameters will also be summarized using descriptive statistics (N, arithmetic mean, standard deviation, standard error, minimum, median, maximum, percent coefficient of variation, geometric mean, and geometric percent coefficient of variation) for each cycle. Also, when appropriate, graphical representations (i.e., scatter plots, box plots, etc.) may be used to visualize the results.

The effect of CC-486 on the PK of durvalumab will be assessed using graphic comparison and descriptive stats.

CCI [REDACTED]

13.3 Immunogenicity

From all subjects dosed with durvalumab, 6 PK and 6 immunogenicity predose samples (Cycle 1, 2, 4, 6, 10, and 14 Day 1), Anti-Drug Antibody (ADA), should have been collected.

By-subject listing of pharmacokinetic and ADA blood sample collection times will be provided. Durvalumab serum concentrations and ADA will be summarized using descriptive statistics (N, arithmetic mean, standard deviation, standard error, minimum, median, maximum, percent coefficient of variation, geometric mean, and geometric percent coefficient of variation).

CCI [REDACTED]

15 APPENDICES

15.1 Appendix A: Date Imputation Guideline

15.1.1 Impute Missing AE start day and month [namely, dd & mm in dd-mm-yyyy are missing]

- If $yyyy(AE) = yyyy(1^{st} \text{ day of study medication})$, then
 - $dd(AE) = dd(1^{st} \text{ day of study medication})$
 - $mm(AE) = mm(1^{st} \text{ day of study medication})$
- If $yyyy(AE) < yyyy(1^{st} \text{ day of study medication})$, then
 - $dd(AE) = 31$
 - $mm(AE) = \text{December}$
- If $yyyy(AE) > yyyy(1^{st} \text{ day of study medication})$, then
 - $dd(AE) = 1$
 - $mm(AE) = \text{January}$

14.1.2 Missing AE start month only [namely, mm in dd-mm-yyyy is missing]

- If $yyyy(AE) = yyyy(1^{st} \text{ day of study medication})$, then
 - $mm(AE) = mm(1^{st} \text{ day of study medication})$
- If $yyyy(AE) < yyyy(1^{st} \text{ day of study medication})$, then
 - $mm(AE) = \text{December}$
- If $yyyy(AE) > yyyy(1^{st} \text{ day of study medication})$, then
 - $mm(AE) = \text{January}$

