Subjects will undergo screening procedures over a period of up to 28 days following the signing of their informed consent document (ICD). Eligible subjects will continue to the safety run-in or the randomized treatment phase of the study where they will receive IP for up to six 28-day treatment cycles. Those who derive benefit from the treatment may continue IP until loss of that benefit (Section 4.1.3).

After treatment discontinuation, subjects will be followed for 28 days for CC-486 safety-related issues and 90 days for durvalumab safety-related issues. After that, subjects will be contacted by telephone every 3 months in the follow-up phase of the study.

The enrollment period for this study is expected to last approximately 39 months. The treatment and follow-up periods are expected to conclude approximately 12 months after the last subject is enrolled. The Extension Phase is expected to last approximately 24 months. Therefore, the total duration of the study is expected to be approximately 75 months.

The *End of Trial* is defined as either the date of the last visit of the last subject to complete the study, or the date of receipt of the last data point from the last subject that is required for primary, secondary and/or exploratory analysis, as pre-specified in the protocol and/or the Statistical Analysis Plan (SAP), whichever is the later date.

The study will conclude once all subjects have completed or discontinued from the Extension Phase.

Study Treatment (Investigational Product – IP)

CC-486 (Oral Azacitidine)

Eligible subjects who are assigned to the monotherapy treatment arm will receive CC-486 at the dose and schedule identified during the safety run-in phase of the study. Dose and schedule may be reduced to manage toxicity or increased as described in Section 8.2. Subjects can continue treatment with CC-486 as long as all protocol-specified re-treatment criteria continue to be met (see Section 8.2.5).

Durvalumab (MEDI4736)

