All AEs will be recorded by the investigator from the time the subject signs informed consent until 28 days after the last dose of CC-486, 90 days after the last dose of durvalumab, or until the Treatment Discontinuation Visit, whichever is later and those SAEs made known to the investigator at any time thereafter that are suspected of being related to IP. Adverse events and SAEs will be recorded on the AE page of the CRF and in the subject's source documents. All SAEs must be reported to Celgene Drug Safety within 24 hours of the investigator's knowledge of the event by facsimile, or other appropriate method, using the SAE Report Form, or approved equivalent form.

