11.1. Adverse Events

Adverse events will be coded using Medical Dictionary for Regulatory Activities (MedDRA) of Version 22. Adverse event listings will include the verbatim term and the MedDRA preferred term. The intensity of AEs will be graded according to the Common Terminology Criteria for Adverse Events (CTCAE) Version 4.03 or higher. For any AE not listed in the CTCAE grading system, the intensity of these events will be assessed by the Investigator using a 5-point scale as described in protocol.

If a subject experiences multiple AEs under the same PT (SOC), the subject will be counted only once for that PT (SOC). If a subject experiences the same AE more than once with a different intensity grade, the event with the highest grade will be tabulated in “by grade” tables. In addition, AEs with a missing intensity will be presented in the summary table as an intensity category of “Missing” and will not be imputed.

Treatment emergent adverse events (TEAEs) are defined as AEs occurring or worsening on or after the date of the first dose of the study treatment (CC-486 or durvalumab) and within 28 days after last dose of CC-486 or 90 days after last dose of durvalumab. A treatment-related TEAE is defined as a TEAE where the causal relationship was assessed by the investigator as “Suspected”. If the relationship between a TEAE and a study drug is missing, the TEAE will be considered to be related to the study treatment.

Summary tables for the incidence of TEAEs will be summarized by disease cohort, treatment arm, SOC, and PT within SOC. They will be sorted by alphabetically order of SOC and PT, and then sorted by decreasing frequencies, unless otherwise specified. Following tables will be generated:

- TEAEs;
- TEAEs related to CC-486 only, durvalumab only, or CC-486 or durvalumab;
- TEAEs of CTCAE grade 3 or 4;
- TEAEs related to CC-486 only, durvalumab only, or CC-486 or durvalumab with CTCAE grade 3 or 4;
- TEAEs with death outcome;
- TEAEs with death outcome related to CC-486 only, durvalumab only, or CC-486 or durvalumab;

- Serious TEAEs;
- Serious TEAEs related to CC-486 only, durvalumab only, or CC-486 or durvalumab;
- TEAEs leading to discontinuation of CC-486 only, durvalumab only, or CC-486 or durvalumab;
- TEAEs leading to dose reduction of CC-486;
- TEAEs leading to dose interruption of CC-486 only, durvalumab only, or CC-486 or durvalumab;
- TEAEs leading to infusion interruption of durvalumab.

As well as

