14.1.3 Missing AE start day only [namely, dd in dd-mm-yyyy is missing]

- If $yyyy(AE) = yyyy(1^{st} \text{ day of study medication})$, then
 - If $mm(AE) = mm(1^{st} \text{ day of study medication})$, then
 - $dd(AE) = dd(1^{st} \text{ day of study medication})$
 - If $mm(AE) > mm(1^{st} \text{ day of study medication})$, then
 - $dd(AE) = 1$
 - If $mm(AE) < mm(1^{st} \text{ day of study medication})$, then

- $dd(AE) = \text{last day of mm}(AE)$
- If $yyyy(AE) < yyyy(1^{\text{st}} \text{ day of study medication})$, then
 - If AE stop date exists and is complete, then
 - $dd(AE) = dd(AE \text{ stop});$
 - if AE stop date does not exist or is incomplete, then
 - $dd(AE) = \text{last day of mm}(AE)$
- If $yyyy(AE) > yyyy(1^{\text{st}} \text{ day of study medication})$, then
 - $dd(AE) = \text{first day of mm}(AE)$

14.2.1 Missing AE stop day and month [namely, dd & mm in dd-mm-yyyy are missing]

- If $yyyy(AE) = yyyy(\text{last day of study medication})$, then
 - $dd(AE) = dd(\text{last day of study medication})$
 - $mm(AE) = mm(\text{last day of study medication})$
- If $yyyy(AE) < yyyy(\text{last day of study medication})$, then
 - $dd(AE) = 31$
 - $mm(AE) = \text{December}$
- If $yyyy(AE) > yyyy(\text{last day of study medication})$, then
 - $dd(AE) = 1$
 - $mm(AE) = \text{January}$

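### SAP Appendix A can give the wrong treatment-emergent status to adverse events with partial start dates, because imputed dates are not checked against first dose or a known stop date

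*SAP*

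**What the plan says.** SAP 11.1 defines TEAEs as "AEs occurring or worsening on or after the date of the first dose of the study treatment" and "within 28 days after last dose of CC-486 or 90 days after last dose of durvalumab". The start date therefore decides whether an event enters the TEAE tables. Protocol 11.1 makes pre-dose events part of the database: "All AEs will be recorded by the investigator from the time the subject signs informed consent". The Protocol Summary (Length of Study) gives the length of that pre-dose period: "Subjects will undergo screening procedures over a period of up to 28 days".

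Appendix A (numbered partly 15.1.1 and partly 14.1.2 to 14.2.3) imputes partial start dates from the first dose:

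- "Impute Missing AE start day and month" (15.1.1): in the first-dose year, the start becomes the first-dose date.
- "Missing AE start month only" (14.1.2): in the first-dose year, the month becomes the first-dose month and the recorded day is kept.
- Day only missing (14.1.3): in the first-dose year and month, the day becomes the first-dose day.

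None of these three branches looks at the stop date. The stop date is used in one start branch only: day missing, with an event year before the first-dose year.

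Stop dates are imputed from the last dose. Under "Missing AE stop day and month" (14.2.1), a stop in the last-dose year becomes the last-dose date, and a stop in a later year becomes 1 January. The start date is consulted only when the day alone is missing and the stop month or year is after the last dose (14.2.3).

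No general rule requires a start to be on or before its stop.

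**The concern.** An imputation rule for start dates should do two things. When the truth is unknown, it should not take possible on-treatment events out of the safety tables. It should also not contradict a date that is known. The branches above fail on one or the other.

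Rule 14.1.2 fails on the first. It combines the first-dose month with a day that may belong to a later month, so an on-treatment event can be dated before first dose. Appendix A is also inconsistent here: a record with less information (day also lost) goes to first dose and counts as a TEAE.

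Rules 15.1.1 and 14.1.3 fail on the second. Sending an unknown start to first dose is ordinary caution. Doing so when a complete stop date shows that the event was over before first dose is not.

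At stake are the outputs in SAP 11.1 that depend on start dates: TEAE incidence, TEAEs by cycle of onset, and the incidence rates for events of special interest.

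**Working it through.** The documents state no figure on this point, so there is none to reproduce. The rules were applied literally to test dates, and the share of affected records was then calculated under stated assumptions.

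**Test dates** (assumed: first dose 20-Mar-2017; last dose 10-Sep-2017 except in the last row)

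| True event | Recorded | Rule | Imputed | Consequence |
|---|---|---|---|---|
| Onset 05-Jun-2017 | start 05-UNK-2017 | 14.1.2 | start 05-Mar-2017 | 15 days before first dose, not a TEAE |
| 01-Mar to 10-Mar-2017 | start UNK-UNK-2017, stop complete | 15.1.1 | start 20-Mar-2017 | TEAE, starts 10 days after it stopped |
| 01-Mar to 10-Mar-2017 | start UNK-Mar-2017, stop complete | 14.1.3 | start 20-Mar-2017 | same |
| 25-Feb to 10-Mar-2017 | start 25-UNK-2017, stop complete | 14.1.2 | start 25-Mar-2017 | TEAE, starts 15 days after it stopped |
| Start 25-Sep-2017 | stop UNK-UNK-2017 | 14.2.1 | stop 10-Sep-2017 | stop before start |
| Start 10-Jan-2018, last dose 20-Dec-2017 | stop UNK-UNK-2018 | 14.2.1 | stop 01-Jan-2018 | stop before start |

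Onsets after the last dose, as in the last two rows, are in scope because the TEAE window runs 28 or 90 days past it.

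**Share of month-only-missing starts dated before first dose.** Rule 14.1.2 gives a pre-dose date exactly when the recorded day is less than the first-dose day. If the two days are independent and uniform on 1 to 30:

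P = (30 × 29 / 2) / (30 × 30) = 435/900 = 0.483.

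This counts every such record, including events that truly began before first dose.

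**Share of true on-treatment onsets misplaced.** This is a different quantity. Assume onsets spread evenly over 168 days (six 28-day cycles) from a first dose in March 2017, with only the month missing:

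| First-dose day of month | 1 | 10 | 15 | 20 | 28 |
|---|---|---|---|---|---|
| Share misplaced | 0% | 27% | 42% | 58% | 87% |

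Averaged over first-dose dates from 1 January to 1 July, the share is about 45%.

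**Reach of rule 15.1.1 for pre-dose events.** Take every first-dose date in a 365-day year and a 28-day screening window. Only first doses on 1 to 28 January have window days in the previous year: 28 + 27 + … + 1 = 406 of 365 × 28 = 10,220 onset days. So 1 − 406/10,220 = 96% of onset days fall in the first-dose year. A start there with day and month missing goes to first dose, whatever its stop date.

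**Effect on a table.** In a Stage 1 cohort of 16, one subject is 1/16 = 6.25 percentage points. SAP 11.1 counts a subject once per preferred term, so the figure moves only if that subject has no other qualifying record of the term.

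**The case against.** Several points can be made for the plan.

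- **The pre-dose date may be right.** A start recorded as 05-UNK-2017 with first dose on 20 March may truly be 5 March, inside the screening window. This stands. A reader might infer that each pre-dose imputation is an error, or that 48% is an error rate. The documents support neither, because the rule is wrong only for events that began on treatment.
- **The event is not lost.** SAP 11.1 still lists all adverse events, and Protocol 10.7 summarises adverse events as well as TEAEs. This stands: the event leaves the TEAE tables, not the report.
- **Sending an unknown start to first dose is conservative.** This stands as a default. It does not justify ignoring a complete earlier stop date, and 14.1.3 already uses the stop date in one branch.
- **Stop-date reversals change no analysis.** This stands. A reader might infer that they distort results, but no planned table is stated to use the stop date and TEAE status depends on the start. The effect is confined to listings.
- **Such records should be rare.** Protocol 11.2.4 asks for start and stop dates, 15.2 provides edit checks and 16.1 provides source verification. A known day with an unknown month is unusual, only 65 subjects were enrolled, and the safety summaries are descriptive. This stands and limits the size of the point.

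None of this removes the defect in the start rules: nothing else in either document overrides them.

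**Conclusion.** The point holds as a minor defect in a stated rule. Applied as written, Appendix A can (a) date an on-treatment event before first dose when only the month is missing, which removes it from the TEAE tables, and (b) make a resolved pre-dose event a TEAE that starts after it stopped. It can also (c) give a stop before its start, in listings only. Of the two effects on TEAE status, (a) is the more serious because it understates treatment-emergent events; (b) overstates them.

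The size is unknown, because neither document says how many dates are partial, and is probably small. The shares given apply only to records with that pattern of missing parts. They rest on uniform days for the 48%, and on uniform onset over six cycles for the 0% to 87% range and its 45% average.

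**What to change.** Amend Appendix A as follows:

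1. Apply the 15.1.1 rule to starts with only the month missing. The record 05-UNK-2017 then goes to 20-Mar-2017 and counts as a TEAE. Some truly pre-dose events will also be counted, which is the cautious direction.
2. Cap any imputed start at the event's stop date when that date is complete. The event that ended on 10-Mar-2017 is then dated 10-Mar-2017 and stays pre-dose, whichever start rule applies.
3. Keep the existing rules that leave a start pre-dose when its known year or month is before first dose. With first dose on 20-Mar-2017, UNK-Feb-2017 should remain 28-Feb-2017 and UNK-UNK-2016 should remain 31-Dec-2016. A blanket rule taking the later of first dose and the earliest compatible date would wrongly turn both into TEAEs.
4. Never impute a stop before the event's start, or after death or data cut-off. The stop of 01-Jan-2018 in the last test row would become 10-Jan-2018.

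The cost is a few lines of SAP text and of programming, with no new data.
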